2.1 Hypotheses

Primary Objective: To investigate the effectiveness of the FoodRx healthy food prescription incentive program in reducing A1C.

H_0 (null hypothesis): the healthy food prescription incentive program **does not** reduce A1C by a clinically meaningful difference of at least 0.5% between the intervention and comparison groups at 12-months.

H_1 (alternative hypothesis): the healthy food prescription incentive program **does** reduce A1C by a clinically meaningful difference of at least 0.5% between the intervention and comparison groups at 12-months.

Secondary and Exploratory Objectives: To investigate the effectiveness of the FoodRx healthy food prescription incentive program in reducing food insecurity, and improving clinical health markers, dietary intake, and patient-reported outcome measures (PROMs).

¹ A comprehensive study protocol has been published (doi:10.1136/bmjopen-2021-050006).

3. Methods

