4.2 Sample Size

The sample size calculation was based on A1C, the primary outcome for the RCT. A mean baseline A1C of 8.5% (SD=1.4%) was expected in our population based on local administrative data.⁴⁴ For 90% power to detect a minimally important clinical difference in A1C of 0.5%⁴⁵, 594 participants were required assuming 5% type 1 error, 30% attrition⁴⁶, and potential design effects based on sampling in different primary care clinics and communities (25% inflation).

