6.5 Multiple Comparisons

We have used current guidelines for multiplicity to assess the risk of increased Type I error rates in this study.^{116, 117} As such, we will not adjust for multiple comparisons given the RCT 1) is exploratory, 2) includes 2 distinct treatment arms, 3) has a single pre-specified primary outcome that is the basis for statistical inference, 4) positions secondary and exploratory outcomes as supportive to the primary outcome and as hypothesis-generating, 5) did not include interim analyses, 6) will account for repeated measures using mixed-effect models with group by time and time-treatment interactions (testing for contrasts at each timepoint)¹¹⁷, 7) includes pre-specified exploratory sub-group analyses, and 8) includes exploratory sensitivity analyses to assess treatment consistency across groups. In addition, multiplicity adjustments increase the chance of type 2 errors, and assume all null hypotheses are true (i.e., all positive results are false positives). Lastly, these adjustments assume all outcomes are independent, which is not the case for the FoodRx RCT as many outcomes are related (e.g., blood lipids, systolic and diastolic blood pressure). All results will be interpreted with caution considering p-values,

confidence intervals, and effect sizes. Findings for secondary results, and secondary and exploratory outcomes will be presented as exploratory.¹¹⁸

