6.6 Statistical Software

Statistical analyses will be conducted in Stata¹¹⁹, and R¹²⁰ using versions specified in the final manuscripts.

7. Analyses

To describe the analyses, we have grouped all outcomes according to the manuscript in which they will be reported. Mixed-effects linear, logistic, and/or non-linear regression models will be used to assess group differences in outcomes at baseline and post-intervention.

The incentive program was paused after 11 weeks due to problems with delivery of the incentive. The incentive program resumed 12 weeks later when the issues were rectified. This restart impacted 31 participants who had completed baseline data collection, been randomized, and begun the program. Those who chose to remain in the program completed baseline data collection a second time, resulting in duplicate baseline measures. The following analyses will include the second set of baseline data unless otherwise specified (i.e., sensitivity analysis).

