7.4 Primary Manuscript

This paper will report results for 12-month A1C, our primary outcome, along with secondary and exploratory outcomes at 6-, 12-, and/or 18-months, including blood glucose levels, clinical health markers, and need for antihyperglycemic medication.

12-month A1C, Primary Outcome

We will assess the intention to treat effect of group assignment on mean A1C at 12-months as a continuous outcome using mixed-effects linear regression. The primary test will be the group \times time interaction contrast at 12-months (i.e., post-intervention), which estimates between-group differences in mean A1C from baseline to 12 months. Models will be adjusted for baseline A1C to estimate treatment effect while holding baseline A1C constant, and additional blocking variables (gender, recruitment location). To improve the precision of effect estimates, models will also be adjusted for age, race/ethnicity, educational attainment, number of children living in the home, and diabetes duration. Additionally, all models will include a data source indicator variable (study measured vs administrative health data), group (FoodRx vs comparison), collection timing (number of days measurement was taken since baseline), and restart cohort indicator variable (did not restart vs did restart). We will include random intercepts for participants (participant study ID) to account for within-subject correlation due to repeated measures, and for primary care clinics (clinic study ID) to account for clustering of participants within clinics. Missing data for covariates will be addressed using full information maximum likelihood.

We will conduct subgroup analyses for 12-month A1C by baseline household food insecurity severity (marginal, moderate, severe), gender (man, woman, gender diverse), recruitment location (urban setting, rural setting, Indigenous primary care clinic), Indigenous identity, baseline A1C ($\leq 8.5\%$, $\geq 8.6\%$), and baseline insulin use (no, yes).

We will conduct dose-response analyses to examine whether 12-month A1C differs based on the total value of incentives redeemed, a continuous variable, in the first 6 months for the mid-intervention analysis, and in the full 12-months for the post-intervention analysis.

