In addition to per-protocol and as-treated analyses, we will conduct sensitivity analyses for 12-month A1C to examine 1) the impact of excluding A1C values obtained from administrative health data, 2) if findings differ when models include all participants regardless of A1C source, and a collection timing indicator variable (time since baseline, deviation from 12-month data collection timepoint), 3) the impact of using multiple imputation for missing data rather than full information maximum likelihood, 4) the impact of adjusting for changes in medication/insulin type and dosage between baseline and post-intervention follow-up, 5) the impact of including the first measure of baseline A1C collected before the trial was restarted, and 6) the impact of excluding participants who restarted the trial.

Blood Glucose Levels, Secondary Outcomes

6-month A1C We will assess group differences in 6-month A1C (i.e., mid-intervention) as a continuous outcome using mixed-effects linear regression. Models will be adjusted for baseline A1C, and additional blocking variables (gender, recruitment location). To improve the precision of effect estimates, models will also be adjusted for age, race/ethnicity, educational attainment, number of children living in the home, and diabetes duration. Models will also include group (FoodRx vs comparison), and baseline A1C data source (study measured vs administrative health data) indicator variables. We will include random intercepts for participants (participant study ID) to account for within-subject correlation due to repeated measures, and for primary care clinics (clinic study ID) to account for clustering of participants within clinics.

In addition to per-protocol and as-treated analyses, we will conduct sensitivity analyses for 6-month A1C to examine 1) the impact of excluding A1C values obtained from administrative health data, 2) if findings differ when models include all participants regardless of A1C source, and a collection timing indicator variable (time since baseline, deviation from 6-month data collection timepoint), 3) the impact of using multiple imputation for missing data rather than full information maximum likelihood, 4) the impact of adjusting for changes in medication/insulin type between baseline and mid-intervention follow-up, and 5) the impact of including the first measure of baseline A1C collected before the trial restart.

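### The primary A1C test is described both as a baseline-to-12-month group × time contrast and as a baseline-adjusted 12-month effect, so the model rows and the tested coefficient are not fixed

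*SAP*

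**What the plan says.** Section 7.4 opens the primary analysis with a 12-month target: "We will assess the intention to treat effect of group assignment on mean A1C at 12-months as a continuous outcome using mixed-effects linear regression". It then makes the group × time contrast at 12 months the primary test, "which estimates between-group differences in mean A1C from baseline to 12 months. Models will be adjusted for baseline A1C to estimate treatment effect" with baseline A1C held constant. Within-person correlation is handled by a participant random intercept, alongside a clinic intercept.

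Other places bear on which rows enter the model:

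- The opening of Section 7 says of all the mixed models: "models will be used to assess group differences in outcomes at baseline and post-intervention".
- Section 2.1 frames the hypothesis as a reduction "by a clinically meaningful difference of at least 0.5% between the intervention and comparison groups at 12-months".
- Section 6.5 speaks of "mixed-effect models with group by time and time-treatment interactions (testing for contrasts at each timepoint").
- The secondary A1C visits have their own paragraphs in Section 7.4, for example "We will assess group differences in 6-month A1C (i.e., mid-intervention) as a continuous outcome using mixed-effects linear regression". These omit the collection-timing and restart terms of the primary model but still carry a participant intercept for repeated measures.

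Section 4.2 sets the size: "594 participants were required assuming 5% type 1 error, 30% attrition", plus 25% inflation for design effects, SD 1.4%, difference 0.5%, power 90%.

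**The concern.** A difference measured from baseline and a difference at fixed baseline are separate analyses. The first puts baseline A1C on the left of the model, the second on the right. The primary paragraph asks for both, and nowhere does the SAP list the A1C rows (0, 6, 12 or 18 months), the coding and reference level of time, or the coefficient that yields the primary p-value.

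That baseline is meant as a row is an inference. It rests on the contrast wording, the Section 7 sentence, and the participant intercept in single-follow-up models, where repeats exist only if baseline is a row. Three readings remain:

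1. Baseline is a row and also a covariate; the test is the group × 12-month interaction.
2. Follow-up rows only, baseline as covariate; the test is the interaction coefficient.
3. Follow-up rows only, baseline as covariate; the test is the group difference at 12 months.

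Section 6.5 declines multiplicity adjustment partly because one pre-specified primary outcome carries the inference. If that test can be fitted three ways with three p-values, the choice may be made after the data are open.

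**Working it through.** **The plan's own figure.** Per arm: 2 × (1.960 + 1.282)² × 1.4² / 0.5² = 165, so 330 in total. 330 × 1.25 / 0.70 = 590; the t-based version (166 per arm) gives 593. The stated 594 therefore reproduces as a comparison of two 12-month means with no credit for baseline, two-sided 5% assumed.

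**Inputs.** Effective n = 594 × 0.70 / 1.25 = 333, or 166 per arm. SD is 1.4. The correlation r between visits is not in the SAP; 0.3, 0.5 and 0.7 are assumed. The clinic intercept is left out.

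**Reading 1, estimate.** With complete data, a covariate constant over a person's rows cancels from a within-person contrast. In one simulated data set with rows 0, 6 and 12, the interaction estimate was −0.01342 with and without the covariate, equal to the raw difference in change; the baseline-adjusted 12-month estimate was −0.06150. The time-varying data-source and timing terms move it only slightly (−0.0502 to −0.0532 in another example). With 30% of 12-month values missing, the covariate does change the estimate (−0.081 to −0.112).

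**Precision and power for 0.5%.** With n per arm, the variance is 2·SD²·2(1−r)/n for change and 2·SD²·(1−r²)/n for the baseline-adjusted difference; their ratio is 2/(1+r).

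| r | Variance ratio | SE, change | SE, adjusted | Power, reading 1 | Power, reading 3 |
|---|---|---|---|---|---|
| 0.3 | 1.54 | 0.182 | 0.147 | 79% | 93% |
| 0.5 | 1.33 | 0.154 | 0.133 | 90% | 96% |
| 0.7 | 1.18 | 0.119 | 0.110 | 99% | 99.5% |

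The reading 1 column uses the true variance of the change contrast. It reaches 90% at r = 0.495.

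**Reading 1, standard error, rows 0 and 12.** In SD² units, the pooled slope on baseline is b = (1+r)/2. The two residuals of one person then have covariance −(1−r)²/4, which is negative, so the participant variance falls to its zero bound (in 100% of simulated fits). The pooled residual variance is (3+r)(1−r)/4 where 1−r is needed, so model SE / true SE = √((3+r)/4) = 0.908, 0.935, 0.962. Type I error is 7.5%, 6.7%, 5.9%.

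Now let a fraction p of participants have a 12-month value. Then b = (1+pr)/(1+p), the baseline residual variance is (1−b)², and the 12-month residual variance is 1+b²−2rb. At r = 0.5 and p = 0.7:

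- b = 0.794; the residual variances are 0.042 and 0.837; pooled, (0.042 + 0.7 × 0.837)/1.7 = 0.369.
- Model SE = √(2 × 1.96 × 0.369 × (1/297 + 1/208)) = 0.109.
- True SE = √(2 × 1.96 × [0.837/208 + 0.042/297 + 2 × 0.206 × 0.294/297]) = 0.134.
- Type I error = 2[1 − Φ(1.96 × 0.109/0.134)] = 11.1%, taking unrounded SEs.

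The near-zero baseline residuals pull the pooled variance down while the contrast depends on the 12-month row. Simulation (REML, 8,000 runs per cell; 208 per arm complete, or 297 per arm with 30% missing completely at random) agrees:

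| Rows | Data | With covariate (r = 0.3, 0.5, 0.7) | Without |
|---|---|---|---|
| 0, 12 | complete | 7.5%, 6.8%, 6.1% | 5.0–5.2% |
| 0, 12 | 30% dropout | 11.4%, 10.9%, 10.6% | 5.0–5.2% |
| 0, 6, 12, equal correlations | complete | 5.2–5.5% | 5.2–5.5% |
| 0, 6, 12, equal correlations | 30% dropout | 6.7%, 6.6%, 6.7% | 5.3%, 5.2%, 5.1% |

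A separate effect: if adjacent visits correlate 0.15 more than the outer pair, three complete visits give 7.4%, 8.4%, 11.6% with or without the covariate. That comes from using only a random intercept, not from using baseline twice.

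**Reading 2.** The coefficient is the 12-month minus the 6-month effect. If the effect is 0.5% at both visits it is 0, and rejection is 5%. If the effect is 0.25% at 6 months and 0.5% at 12, the target is 0.25% with SE √(2·SD²·2(1−r)/n) = 0.182, 0.154, 0.119, so power is 28%, 37%, 56%.

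**The case against.** The strongest reply is that the SAP leans towards reading 3. The hypothesis, the opening of the primary paragraph, the outcome definition in Section 5.1 and the adjustment rule in Section 7.2 all fit a baseline-adjusted 12-month difference. Against them stand one subordinate clause and a loose sentence in Section 7 that omits 6 months altogether. The participant-intercept sentence is repeated even for the cumulative medication score, so it says little about rows. This makes reading 3 the likelier intention, but that clause is the definition of the primary test, and reading 3 contradicts it.

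Reading 2 may look contrived, since it too conflicts with that clause. It is nevertheless what testing the named interaction yields once baseline is taken out of the rows.

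The error-rate argument is fairly narrowed. The 11% needs rows at 0 and 12 only and the full 30% loss, whereas Section 5.1 fills missing A1C from records within 3 months. With 10% missing (p = 0.9 in the formulas above) type I error is 8.5%, 7.8%, 7.2%, so backfilling shrinks the excess without removing it. With a 6-month row and equal correlations there is no excess with complete data. Reading 1 is also unbiased under randomization, and it misses the planned 90% power only if r is below about 0.5.

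**Conclusion.** The concern holds: the stated rule for the only confirmatory test contradicts itself, and no other section resolves it. This must be fixed before analysis.

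What is certain is that the readings are different tests, and that under reading 1 with complete data the promised baseline adjustment does not reach the estimate. The size of the harm depends on the rows chosen, on r and on missingness. Under reading 1 it runs from lost precision alone to a type I error of about 11%; under reading 2 a sustained effect can be missed entirely. The sample size of 594 is not in dispute.

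**What to change.** State in Section 7.4 the outcome rows, the coding of time, and the single coefficient or contrast that gives the primary p-value. Either of two standard forms will do:

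- **Baseline-adjusted follow-up model.** Post-baseline A1C rows only; baseline A1C as covariate, interacted with visit; primary test is the group difference at 12 months.
- **Constrained longitudinal model.** Baseline in the outcome vector with a common mean in both arms; no baseline covariate; primary test is the group × 12-month coefficient.

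Remove the from-baseline description if the first is chosen, and the covariate adjustment if the second is. Use an unstructured visit covariance, which also deals with the random-intercept problem. If only one follow-up row is modelled, drop the participant intercept, which cannot then be separated from the residual. Align the general sentence in Section 7, and state rows and contrast for the other outcomes, whose paragraphs adjust for baseline but name no interaction.

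The cost is SAP wording and model code. No new data are needed.

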5.1 Primary Outcome

T2DM is a chronic metabolic disorder characterized by high blood glucose levels resulting from insulin resistance and/or impaired insulin secretion by the pancreas.⁴⁷ Monitoring blood glucose is essential to effective T2DM management. In this study, glycemic control was primarily quantified using A1C, which reflects average blood glucose levels over the previous 3 months.⁴⁸ An absolute reduction of 0.5% in A1C is achievable through improving diet quality^{8, 9} and is considered a clinically meaningful difference.⁴⁵ The 12-month FoodRx program provided adequate time to see dietary changes in 4 A1C cycles.

² *Indicates this characteristic was added after protocol registration.

The priority source for A1C will be blood samples, which participants provided at an Alberta Precision Laboratory or DynaLIFE Medical Lab of their choice. Blood sample collection and testing were standardized to the Diabetes Complications and Control Trial.⁴⁹⁻⁵² When A1C results are not available from blood samples participants' provided specifically for the RCT, we will extract A1C results from medical records and/or the Alberta Health Services' Analytics Data Integration, Measurement, and Reporting database. For extracted A1C, we will use results that were collected 3 months before or after the time point of interest (e.g., 3 months before or after the participant's post-intervention lab collection date). We will analyze 12-month A1C as a continuous outcome.

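### The primary 12-month A1C model adjusts for collection timing, and for a data source not limited to baseline; timing is set after randomisation and source may be, so the intention-to-treat contrast can be biased

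*SAP*

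**What the plan says.** SAP Section 7.4 sets the aim of the primary analysis: "We will assess the intention to treat effect of group assignment on mean A1C at 12-months". The test is the group-by-time contrast at 12 months from a mixed-effects linear model. Beside baseline covariates, the model contains two measurement terms. The SAP states that "all models will include a data source indicator variable (study measured vs administrative health data"), and it adds "collection timing (number of days measurement was taken since baseline").

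Section 5.1 explains how a value comes to be administrative: "When A1C results are not available from blood samples participants' provided specifically for the RCT, we will extract A1C results from medical records" or from a provincial database. For these the plan accepts "results that were collected 3 months before or after the time point of interest".

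The 6-month A1C model in the same section uses a narrower term, "baseline A1C data source (study measured vs administrative health data) indicator variables", and has no timing covariate in its main form. The other Section 7 models that carry a source term also limit it to baseline.

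Sensitivity analysis 2 for 12-month A1C asks "if findings differ when models include all participants regardless of A1C source, and a collection timing indicator variable". Section 3.4 says that participants knew their allocation. Section 6.2 promises unadjusted as well as adjusted estimates.

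**The concern.** Randomisation protects a comparison adjusted for things fixed before allocation. It does not protect one adjusted for things that allocation can change.

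- **Timing.** Days since baseline carries information only for values taken after baseline, so it is post-randomisation on any reading.
- **Source.** If the indicator describes the 12-month value, then by Section 5.1 it records whether the participant gave a study blood sample. One arm received a weekly incentive for a year and knew it, so a difference between arms in willingness to attend is plausible.

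Suppose arm affects either variable, and health or engagement affects both that variable and A1C. Holding the variable fixed then compares participants who differ in health, and some of that difference is read as treatment effect. At stake is the single estimate on which the trial's inference rests.

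The plan is also inconsistent. Timing is already in the primary model, yet it returns as the feature that sensitivity analysis 2 is meant to introduce. Days since baseline also overlaps heavily with the time factor that defines the contrast.

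**Working it through.** **Scale.** SAP Section 4.2 gives SD 1.4, difference 0.5, 90% power, 5% type 1 error (taken as two-sided), 25% inflation and 30% attrition.

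- Per arm: 2 × (1.960 + 1.282)² × 1.4² / 0.5² = 164.8, so 165.
- Total: 330 × 1.25 / 0.70 = 589. With a t-based 166 per arm, 332 × 1.25 / 0.70 = 592.9, or 594 in equal arms. The stated 594 is reproduced.
- Effective size: 594 × 0.70 / 1.25 / 2 = 166 per arm. Standard error of the difference: 1.4 × √(2/166) = 0.154.

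**Source term.** The SAP gives no source rates by arm, so every mechanism value here is an assumption. The simulated model regresses 12-month A1C on arm and baseline A1C at one time point, with and without a 12-month source indicator. An unmeasured health factor is worth 0.6 A1C points per SD. The true effect is -0.5, the incentive arm gives more study samples, and healthier participants are likelier to give one.

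| Study-sample rates | Odds ratio per SD of health | Bias, health factor independent of baseline A1C | Bias, baseline A1C also reflects it |
|---|---|---|---|
| 85% vs 70% | 1.5 | +0.035 | not run |
| 85% vs 70% | 2 | +0.059 | +0.024 |
| 85% vs 70% | 3 | +0.083 | +0.035 |
| 90% vs 60% | 2 | +0.116 | not run |
| 90% vs 60% | 3 | +0.162 | +0.064 |

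A repeat of the last independent setting gave +0.17. Without the source term the true effect is recovered. If source does not depend on arm, or shares no cause with A1C, the bias is nil. With rates of only 85% vs 80% and an odds ratio of 2, it is about +0.01 to +0.02. A true null with 85% vs 70% and an odds ratio of 2 is estimated at about +0.06.

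**Timing term.** Let the incentive arm be measured a days earlier. Let worse health delay measurement by b days per SD and raise A1C by g points per SD. Let the remaining spread in timing have SD s. In a linear model, adjusting for timing shifts the arm coefficient by

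bias = g × b × a / (b² + s²).

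With g = 0.6 and s = 30 days (assumed):

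- a = 7, b = 10: 0.6 × 10 × 7 / (100 + 900) = 0.042
- a = 7, b = 20: 0.6 × 20 × 7 / (400 + 900) = 0.065
- a = 14, b = 10: 0.6 × 10 × 14 / 1000 = 0.084
- a = 14, b = 20: 0.6 × 20 × 14 / 1300 = 0.129

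A separate simulation over the same day shifts estimated -0.50 at -0.45 to -0.34, a bias of 0.05 to 0.16. Across the checks the range is about 0.03 to 0.17. The bias is proportional to g, so it shrinks when baseline covariates already carry the shared cause. It is zero when a = 0 or b = 0.

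**Against the target.** 0.02 / 0.5 = 4% and 0.17 / 0.5 = 34%. The top of the range is about one planned standard error (0.17 / 0.154 = 1.1). In the directions assumed, the bias is towards no effect; opposite dependence would reverse it.

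**The case against.** - **Source may simply be missing a word.** Section 7.4 never says that the primary model's indicator describes the follow-up value. The parenthesis is the same as in the models that say baseline, so an omission is possible. This stands: for source, what the text proves is an undefined covariate. The follow-up reading is an inference from the missing word, the neighbouring timing term and Section 5.1. The argument does not touch timing.
- **The simulated model is not the planned one.** The plan is a repeated-measures model with participant random intercepts. One version with 6- and 12-month values and a source term per visit gave about 0.02 to 0.07, and about 0.01 to 0.03 when baseline A1C also reflects the health factor. The reduction depends on the assumed within-person correlation, but the direction of this point stands.
- **Unadjusted estimates are promised in Section 6.2.** A reader might infer that no estimate free of these terms is planned. That is not so, and the unadjusted result would help to reveal a distortion. It is not the primary test, however, and no listed analysis clearly keeps the baseline covariates while removing both terms.
- **Sensitivity analysis 2.** A reader might infer that it repeats both terms. It names only timing; being open to any source describes who is included and is not a covariate. It may even be a model without a source term.
- **Sources may differ systematically in measurement.** That could motivate a source term, but the SAP states no such difference, and a sensitivity analysis can address it.

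**Conclusion.** The point holds in a limited form. The primary model contains one covariate that is certainly post-randomisation (timing) and one that probably is (source), although the analysis is described as intention-to-treat. Bias arises only if arm affects one of them and that variable shares a cause with A1C, or A1C itself drives it; the SAP neither shows nor rules this out. Under the stated assumptions the size is about 0.02 to 0.17 A1C points for source and 0.03 to 0.17 for timing, and possibly less in the planned model.

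The documents do not support the stronger reading that the primary effect is biased, or biased by a known amount: no source or timing figures by arm are given. Sensitivity analysis 1 does not settle the matter, because excluding administrative values selects on the same source variable. The sample size is unaffected.

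**What to change.** In SAP Section 7.4, primary 12-month A1C model:

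1. Specify the source indicator as the baseline A1C data source, as the other Section 7 models do.
2. Remove collection timing and any follow-up source term from the primary model.
3. Keep timing in sensitivity analysis 2, and add 12-month data source there by name, since it is not now listed. This also reconciles the primary model with its sensitivity analysis.
4. Tabulate 12-month data source and collection timing by arm, so that readers can see whether either depends on allocation.

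The cost is SAP wording and at most a slight loss of precision. The change should be made before the primary model is run.
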